## 2.5.2 Statistical hypothesis, model, and method of analysis

For region-level CLR, the observations (regions positive/negative status) are clustered within a participant. Observations within participants (clusters) are correlated, which may lead to biased estimates of region-level CLR when the correlated nature of the data within each cluster is ignored. More important, an analysis ignoring correlation often yields a misleading small estimated standard error (and 95% CI) for CLR because it erroneously counts all observations as independent observations. Region-level CLR adjusted for correlation among observations within participants can be modeled by using a logistic regression model with random effects (Gatsonis CA 1995, Verbeke G, Molenberghs G 2000).

When calculating CLR, the number of TP regions  $(y_i)$ , follows the binomial distribution with parameter  $(n_i, p_i)$ ,

$$y_i|b_i\sim \text{Binomial}(n_i,p_i)$$

 $p_i$  denotes the probability of TP among all positive PET regions (TP or FP) for participant i, and  $n_i$  corresponds to the denominator in the CLR definition, i.e. the number of all regions containing at least one PET-positive finding by central assessments (TP or FP regions) for participant i.

The number of TP and FP regions overall (i.e. across all five regions, which are prostate region, PLN, skeletal, extra-pelvic lymph nodes and visceral) and by region across all participants in the EFF will be presented, along with region-level CLR and two-sided 95% CIs estimated using the following logistic regression model with random effects.

$$\log\left(\frac{p_i}{1-p_i}\right) = \mu + b_i$$

where  $p_i$  is the region-level CLR for participant i,  $\mu$  is the fixed effect of overall mean,  $b_i$  is the random effect for participants (clusters).  $b_i$  follows a normal distribution:  $b_i \sim N(0, \sigma_h^2)$ .

The lower bound of the 95% CI should be greater than 0.50 to attain the first co-primary endpoint.

**For patient-level PPV**, the number of TP and FP participants, as well as the number of positive and negative (and inconclusive, if applicable) [F]CTT1057 PET/CT scans, will be presented, along with patient-level PPV with two-sided exact binomial 95% CIs (Clopper and Pearson 1934).

The lower bound of the 95% CI for patient-level PPV should be greater than 0.20 attain the second co-primary endpoint.

The same analysis for patient-level PPV will be repeated by CTS Level.

An individual PET reader will be considered successful if he/she meets the predefined thresholds for both co-primary endpoints, and at least two of three readers should be successful for overall study positivity.

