A central read of the [18F]CTT1057 PET/CT scans will be performed at a CRO by three independent nuclear medicine physicians or radiologists experienced in reading PET, who will be blinded to patient data, including the clinical condition of the patient, results of histopathology/biopsy, results of conventional imaging and PSA levels. Patients and regions will be graded on a two-point scale by each reader (0 = negative; 1 = positive). The 3 PET readers' results will be individually compared to the SoT to generate per-reader performance. An individual PET reader will be considered successful if he/she meets the predefined thresholds for both co-primary endpoints, and at least two of three readers should be successful for overall study positivity.

Regions defined for this study are prostate region (comprising prostate bed/prostate gland and any local invasion of the urinary bladder, rectum or seminal vesicles), PLN region, extra-PLN region, skeletal region and visceral region.

The criteria to be applied for PET positivity is the following:

- A patient will be judged positive if at least one lesion in any region is visually positive.
- A region will be judged as positive if at least one lesion in the region is visually positive.
- Visually PET positive lymph nodes will be considered greater than blood pool (adjacent or mediastinal blood pool)
- PET positive bone lesions will be considered greater than physiologic bone marrow
- PET positive prostate, prostate bed and visceral lesions will be considered greater than physiologic background activity of the involvement organ or anatomic site, as previously described (Eiber et al 2015, Ceci et al 2015, Fendler et al 2019).

Consistency of the PET scan interpretation both between different readers and within readers is an important issue in medical imaging, as it affects portability of results between institutions and may affect patient care. The degree of inter- and intra-reader variability in the qualitative assessment of [18F]CTT1057 PET/CT images will be assessed as a secondary endpoint to ensure consistency of interpretation and hence reliable diagnosis, which has pivotal role in the patient management.

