Two-sided 95% CIs for (overall) region-level diagnostic performance parameters will be calculated using a logistic random-effects models taking into account the correlation among regions within a participant.

For different regions (i.e. prostate region, PLN, extra-pelvic lymph nodes, skeletal, and visceral), two-sided exact binomial 95% CIs for region-level diagnostic performance parameters will be calculated.

Concordance between [18F]CTT1057 and [68Ga]Ga-PSMA-11 for detection of lesions and positive percent agreement will be calculated to assess the concordance.

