# 3.1 Primary endpoints(s)

This study is planned to recruit approximately 190 participants. The sample size calculation is based on the co-primary endpoints of region-level CLR and the patient-level PPV of [18F]CTT1057.

The assumptions for sample size calculations are based on the estimates from data available from prior studies.

The primary endpoint is to evaluate region-level CLR (prostate region, PLN, extra-pelvic lymph nodes, skeletal, and visceral) and patient-level PPV of [F]CTT1057 PET for detection of tumor location confirmed by CTS. Based on the results of previous studies, the following distribution of disease across regions are anticipated: Prostate bed: 30%, pelvis: 15%; extrapelvic soft tissue: 20%; bone metastases: 35% (Eiber et al 2015, Ceci et al 2015, Van Leeuwen et al 2016). It is anticipated that the CLR for the five regions and for all regions combined using conventional imaging ranges from 30-60%. An overall CLR for [F]CTT1057 PET of at most 50% will be considered as unacceptably low. Hence, the null hypothesis that the CLR is at most 50% will be tested against the alternative hypothesis that the CLR is greater than 50%.

The BCR population targeted in this study is expected to have similar PSA values as prior studies (Morris et al 2020) of approved diagnostic PET agents for PCa such as [F]-fluciclovine, which had a 27% PPV for patients with PSA values that were less than 1.78, as noted in their summary basis of approval. Thus, a patient-level PPV of 20% will be considered as unacceptably low. The [F]CTT1057 positive patient rate (detection rate) for the study population is 80% based on [F]-fluciclovine studies. The sample size calculation will be performed based on the null and alternative hypotheses as follows.

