#### 5.4 Statistical models

## 5.4.1 Analysis supporting primary objective(s)

For region-level CLR, statistical model details are presented in Section 2.5. The GLIMMIX procedure in SAS will be used to implement the logistic regression model with random effects.

This analysis will be restricted to participants with at least one PET positive region (TP or FP) by central assessments in the EFF. In case of problems with fitting the model and estimating parameters, the default estimation technique (i.e. residual pseudo-likelihood with a subject expansion (METHOD = RSPL)) will be used. This analysis will be applied to each of the three central readers via the (BY READER) statement.

For this model, the SAS code will be:

```
proc glimmix data=dataset;
by reader;
  class subject;
  model tpcount / poscount= / solution;
  random intercept / subject=subject;
run;
```

- tpcount refers to the number of TP regions per participant
- poscount refers to the number of PET positive regions (TP or FP) per participant

The estimated fixed effect  $\hat{\mu}$  and its standard error SE on the logit scale can be obtained from the output. And the (subject-specific) region-level CLR (conditional on the random effect when  $b_i = 0$ ) along with the two-sided 95% CI can be computed by applying the inverse link function:

Point estimate of the region-level CLR: 
$$E[p_{i}|\hat{b}_{i}=0] = E\left[\frac{y_{-}i}{n_{-}i}|\hat{b}_{i}=0\right] = \frac{\exp(\hat{\mu})}{1+\exp(\hat{\mu})}$$

$$CI_{Lower} = \frac{\exp(\hat{\mu}-z_{0.975}SE)}{1+\exp(\hat{\mu}-z_{0.975}SE)}$$

$$CI_{Upper} = \frac{\exp(\hat{\mu}+z_{0.975}SE)}{1+\exp(\hat{\mu}+z_{0.975}SE)}$$

For patient-level PPV, an exact binomial confidence interval (implemented using SAS procedure FREQ with EXACT statement for one-way tables) will be calculated (Clopper and Pearson 1934)

[figure not shown]
Efficacy endpoints be summarized in terms of percentage rates with 95% CIs.

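### By-region CLR is assigned a participant random-intercept model although each participant gives at most one result per region, so a region that is all true positive (or all false positive) gets no usable interval

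*SAP*

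**What the plan says.** SAP 2.5.2 introduces the random-effects model because regions within a participant are correlated. Its overall analysis runs "across all five regions, which are prostate region, PLN, skeletal, extra-pelvic lymph nodes and visceral". The same sentence goes on to single regions and ties both outputs to one model. It promises counts of TP and FP results not only overall but also "and by region across all participants in the EFF will be presented, along with region-level CLR and two-sided 95% CIs estimated using the following" equation. That equation is logit(p_i) = μ + b_i, with b_i normal with variance σ_b².

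Protocol 4.1 fixes the unit of observation: "A region will be judged as positive if at least one lesion in the region is visually positive". SAP 5.4.1 adds: "This analysis will be applied to each of the three central readers via the (BY READER) statement". The printed GLIMMIX code has no BY-region run and no METHOD= option. The reported CLR is the inverse logit of μ, i.e. conditional on b_i = 0, with Wald limits back-transformed from the logit scale. For fitting problems, SAP 5.4.1 says "the default estimation technique (i.e. residual pseudo-likelihood with a subject expansion (METHOD = RSPL)) will be used".

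For single regions under the secondary endpoints, SAP 2.6.1 takes a different route: "two-sided exact binomial 95% CIs for region-level diagnostic performance parameters will be calculated". SAP 2.6.2 repeats it and lists the parameters as sensitivity, specificity, negative predictive value and accuracy. CLR is not on that list.

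**The concern.** The reason for the random effect is that one participant can contribute several regions. Once the analysis is restricted to one region and one reader, that reason is gone: every contributing participant has n_i = 1. Two things follow.

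- The data determine only the marginal probability of a TP. They cannot separate μ from σ_b, yet the reported quantity is a function of μ alone.
- If every PET-positive result in a region is TP (or every one is FP), μ runs to infinity and the Wald formula has nothing finite to work with.

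By-region CLR is the breakdown of a co-primary endpoint that shows where the tracer localises correctly. The SAP has no rule for an all-TP, all-FP or very sparse region, so a method would have to be chosen after a fit had failed.

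**Working it through.** **The plan's own figures.** The only CLR figures given are for the overall CLR (SAP 3.1), and they reproduce.
- n = σ²(z₀.₉₇₅ + z₀.₉₀)²/(p₁ − p₀)² = (1/12)(1.960 + 1.282)²/0.08² = 136.8, so 137 participants.
- 137/0.80 = 171.25, so 172 enrolled.
- Power at 152 evaluable: Φ(0.08/√((1/12)/152) − 1.96) = 0.927.

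None of this concerns single regions. The documents give neither region counts nor region-specific CLR, so the counts and CLRs below are illustrative assumptions.

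**Identifiability with n_i = 1.** The marginal probability is π = E[expit(μ + σ_b Z)], with Z standard normal. The likelihood is π^k(1 − π)^(n−k), so any pair (μ, σ_b) giving π = k/n fits equally well. For k = 36 of n = 45, the maximised log-likelihood is 36 ln 0.8 + 9 ln 0.2 = −22.518 at every σ_b:

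| σ_b | CLR at b = 0 |
|---|---|
| 0 | 0.800 |
| 0.5 | 0.811 |
| 1 | 0.839 |
| 2 | 0.903 |
| 3 | 0.949 |
| 5 | 0.989 |

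**What the printed code would return.** RSPL is the GLIMMIX default, and it was re-implemented for n_i = 1. It does return an answer, but its variance estimate carries no information. With 40 participants and a true σ_b of 0, 1 or 2, the median estimate of σ_b² was 0.109, 0.109 and 0.107. The intervals are nevertheless sensible away from the boundary:

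| TP/positive | RSPL 95% CI | Clopper-Pearson 95% CI |
|---|---|---|
| 36/45 | 0.657-0.893 | 0.654-0.904 |
| 30/40 | 0.593-0.861 | 0.588-0.873 |
| 23/40 | 0.418-0.719 | 0.409-0.730 |

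**At the boundary.** For 3/3, 5/5 and 10/10 the same algorithm diverges. If iteration stops early, the Wald interval is about 0 to 1; for 5/5 stopped at μ = 5 it is 0.003-1.000. Clopper-Pearson gives lower limits of 0.292, 0.478 and 0.692, each with an upper limit of 1.

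**How often.** The chance that all m positive regions of a type are TP is CLR^m:

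| Assumed true CLR | m = 5 | m = 8 | m = 20 |
|---|---|---|---|
| 0.58 (planning alternative for overall CLR) | 7% | 1.3% | about 0% |
| 0.70 | 17% | 5.8% | 0.1% |
| 0.80 | 33% | 17% | 1.2% |
| 0.90 | 59% | 43% | 12% |

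**The case against.** **The sentence may mean the overall CLR only.** In SAP 2.5.2, the words on overall and by region attach grammatically to the counts. The definition of n_i, the 0.50 threshold and the 5.4.1 code all fit the pooled analysis. This is a possible reading. On it, however, by-region CLR has no stated CI method, so the text still needs an amendment.

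**The sponsor's single-region method is already visible.** Protocol 12.5.1 and SAP 2.6.1 and 2.6.2 use binomial or exact limits by region, and CLR is itself described as a region-level PPV. This shows that the fix is in keeping with the plan. It does not place CLR on the 2.6.2 list, and 2.5.2 attaches a different model to it.

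**The drift from 0.80 to 0.99 is not what the code would print.** This stands. A reader might infer that by-region estimates will be materially wrong in general. They will not under the printed code, because RSPL stays close to the exact result away from the boundary. The fallback wording hints at some other first-choice method, but none is named.

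**The high boundary risks depend on a high assumed CLR.** This also stands, which is why a range is shown. A reader might go further, count a missing interval as a failure to cover, and quote 53% coverage at CLR 0.90 with 8 regions. That mixes two things: among data sets that do yield an interval, a plain logit Wald interval covers about 93%.

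**Visceral disease may not be sparse.** The planning distribution is "Prostate bed: 30%, pelvis: 15%; extrapelvic soft tissue: 20%; bone metastases: 35", which sums to 100% with no separate visceral entry. A reader might conclude that the visceral region is sure to be nearly empty. The soft-tissue group may include visceral disease, so sparsity is plausible but not established.

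**Conclusion.** Wrong as written, minor severity. On the natural reading of SAP 2.5.2, a clustered-data model is assigned to data with no clusters. It has no usable answer when a region is all TP or all FP, and the stated fallback does not help because it is already in force. On the narrower reading, the interval method for by-region CLR is missing.

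The practical harm is confined to sparse or boundary regions. How likely those are depends on counts and CLRs that the documents do not give: with 8 positive regions, from 1.3% at CLR 0.58 to 43% at 0.90.

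The point does not reach the success rule. That rule uses the overall CLR, where a participant can contribute several regions, and the planned sample size stands. Nor does it carry over in general to the by-region positive percent agreement in SAP 2.6.2, which is counted in lesions and can have several per participant within a region.

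**What to change.** In SAP 2.5.2, restrict the random-effects model to the overall CLR (five regions combined). For each single region and each reader, report TP/(TP + FP) with a two-sided Clopper-Pearson 95% CI, the method that SAP 2.6.1 and 2.6.2 already use by region for sensitivity, specificity, negative predictive value and accuracy.

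The cost is one amended sentence and reuse of the PROC FREQ exact method already specified in SAP 5.4. Exact limits are slightly conservative. In return, every region with at least one PET-positive result gets an interval, including an all-TP or all-FP one.

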12.4.2 Statistical model, hypothesis, and method of analysis

To address the co-primary efficacy objectives:

Region-level CLR and its 95% CI will be calculated using logistic random-effects models taking into account the correlation among regions within one patient. .The lower bound of the 95% CI for CLR should be greater than 0.5 to attain the first co-primary endpoint.

Patient-level PPV and its 95% CI will be calculated based on the binomial distribution. The lower bound of the 95% CI for patient-level PPV should be greater than 0.2 to attain the second co-primary endpoint.

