#### 2.5.1 **Primary endpoint(s)**

The co-primary endpoints evaluated for participants in the EFF are the following:

Region-level CLR: Proportion of regions containing at least one TP lesion (anatomically localized correspondence between PET imaging and the reference standard), regardless of any co-existent FP findings within the same region, out of all regions containing at least one PETpositive finding by central assessments. See Section 1.2.1 for Primary Estimand.

Patient-level PPV: Proportion of participants who have at least one TP lesion (anatomically localized correspondence between PET imaging and the reference standard), regardless of any co-existent FP findings, out of all participants who are PET/CT scan positive by central assessments. See Section 1.2.1 for Primary Estimand.

Centralized imaging assessments (CTS Level 2) will be used as reference standard if pathology assessment (CTS Level 1) is not available for a lesion, inconclusive or negative (for biopsy only).

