#### **Region-level CLR**

Correlated binary test results occur in this situation where each experimental unit (participant) consists of five correlated regions. Lee and Dubin developed a sample size formula for clustered binary data (Lee and Dubin 1994). They propose estimating the binary proportion by assigning equal weights to clusters regardless of their sizes to simplify the derivation of their sample size

formula. The weighted estimator for region-level CLR is approximately Gaussian distributed with a variance of a beta distribution (beta-binomial model).

The null hypothesis (H0: region-level CLR p = 0.50) will be tested against the alternative hypothesis (H1: p > 0.50). Assuming a CLR of 0.58 under the alternative hypothesis, a total sample size of 172 enrolled participants would achieve 90% statistical power to detect a change in CLR of 0.08 using a one-sided test at a target significance level of 2.5%. This sample size includes an adjustment for a dropout rate of 20%.

The sample size was determined as n to ensure a type I error using a one-sided significance level of 2.5% and with 90% power to reject H0 if the alternative H1 is true.

By the standard normal approximation, the sample size is given as follows:

$$n = \frac{\sigma^2 (Z_{\alpha} - Z_{1-\beta})^2}{(p_1 - p_0)^2}$$

where  $\sigma^2$  is the variance of a beta distribution,  $Z_a$  is the upper quantile of the standard normal distribution,  $p_0$  is a CLR of 0.50 under the null hypothesis, and  $p_1$  is a CLR of 0.58 under the alternative hypothesis.

Suppose there is no information on the within-cluster correlation of test results. In this case, a uniform distribution seems reasonable, setting parameters in the beta distribution of alpha=1 and beta=1. Then  $\sigma^2$  is 1/12.

Under these assumptions, 137 participants will be necessary to ensure 90% power. Taking into account a 20% dropout rate, a total of 172 participants will be recruited for this endpoint of the study.

The lower bound of the 95% CI for CRL should be greater than 0.50 to be considered a success.

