#### **Patient-level PPV**

The null hypothesis (H0: patient-level PPV p = 0.20) will be tested against the alternative hypothesis (H1: p > 0.20). Assuming a patient-level PPV of 0.33 under the alternative hypothesis, a total sample size of 190 enrolled participants (which includes 152 [ $^{18}$ F]CTT1057 scanned participants based on 80% [ $^{18}$ F]CTT1057 positive patient rate) would achieve 90% power to detect a change in patient-level PPV of 0.13 using a one-sided binomial test at a targeted significance level of 2.5%. This sample size includes an adjustment for a dropout rate of 20%.

The lower bound of the 95% CI for patient-level PPV should be greater than 0.20 to be considered a success.

A total sample size of 190 participants can ensure 92.7% statistical power for region-level CLR and 90% statistical power for patient-level PPV resulting in an overall study statistical power of at least 83.4% (0.927\*0.90).

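### The planned PPV of 0.33 cannot hold beside the planned CLR of 0.58 under the sample-size estimator, and the 0.20 PPV bar is in practice implied by the 0.50 CLR bar

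*SAP*

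**What the plan says.** SAP 2.5.1 defines both co-primary endpoints on PET-positive findings. CLR is the share of regions with a true-positive (TP) lesion, "out of all regions containing at least one PETpositive finding by central assessments". PPV is defined as "Patient-level PPV: Proportion of participants who have at least one TP lesion", "out of all participants who are PET/CT scan positive by central assessments". Co-existing false-positive (FP) findings are disregarded in both.

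SAP 2.5.2 sets the CLR bar at a lower 95% limit above 0.50. For PPV, "The lower bound of the 95% CI for patient-level PPV should be greater than 0.20 attain the second co-primary endpoint"; Protocol 12.4.2 agrees: "The lower bound of the 95% CI for patient-level PPV should be greater than 0.2 to attain the second co-primary endpoint". A reader succeeds only by meeting both bars, and two of three readers must succeed.

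SAP 3.1 and Protocol 12.8.1 give the planning values. For CLR: "Assuming a CLR of 0.58 under the alternative hypothesis". For PPV: "Assuming a patient-level PPV of 0.33 under the alternative hypothesis". The 0.20 bar is motivated by another tracer, "which had a 27% PPV for patients with PSA values that were less than 1.78". Overall power is stated as at least 83.4%, the product of 0.927 and 0.90. Neither document relates the two endpoints or the two planning values to each other.

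**The concern.** The endpoints are nested. A participant enters both only if PET-positive, and a single TP lesion is enough for PPV, while CLR also counts that participant's other positive regions against the tracer. PPV should therefore be the higher of the two. The plan has it the other way round, both in the assumed values (0.33 against 0.58) and in the bars (0.20 against 0.50).

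Two things are at stake. First, the stated PPV power and overall power are calculated at a pair of values that the sample-size estimator rules out. Second, PPV is the endpoint closest to the trial's clinical question, namely whether a positive scan truly detects and localizes recurrence. If its bar is met almost automatically once CLR passes, reporting two co-primary endpoints met overstates the patient-level evidence.

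**Working it through.** **Inputs.** Endpoint definitions are from SAP 2.5.1. A patient is PET-positive if any lesion in any region is visually positive (Protocol 4.1). The CLR model is restricted to participants with at least one PET-positive region (SAP 5.4.1), so both endpoints use the same participants. From SAP 3.1: an equal-weight (participant-averaged) CLR estimator, CLR 0.50 against 0.58, variance 1/12, PPV 0.20 against 0.33, one-sided 2.5%, 80% PET-positive, 20% dropout.

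**1. The plan's figures reproduce.**
- CLR: n = (1/12)(1.960 + 1.282)² / 0.08² = 136.8, so 137; 137/0.8 = 171.25, so 172 enrolled.
- CLR power at 152: z = 0.08 × √(12 × 152) − 1.96 = 1.457, giving 92.7%.
- PPV: 152 × 0.80 = 121.6 PET-positive. With 122 and an exact one-sided binomial test, success needs 34 TP participants (34/122 = 27.9%); alpha is 0.0228 and power at 0.33 is 0.905. With 121, power is 0.894.
- 152/0.8 = 190 enrolled; 0.927 × 0.90 = 0.834.

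The arithmetic is right; the problem is in the assumed values.

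**2. Ordering under the sample-size estimator.** Let participant i have y TP regions out of n PET-positive regions. The participant adds y/n to the equal-weight CLR and adds 1 to the PPV count if y ≥ 1, otherwise 0. If y = 0 both are 0; if y ≥ 1 then y/n ≤ 1. Averaging over the same participants gives PPV ≥ CLR in every data set, with equality only when nobody mixes TP and FP regions. A CLR of 0.58 therefore forces PPV ≥ 0.58.

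**3. The 0.20 bar under that estimator.** If the lower limit for participant-averaged CLR exceeds 0.50, observed PPV exceeds 0.50. Its exact lower limit is then at least 0.41 with 121 or 122 participants. A limit at or below 0.20 with PPV above 0.50 occurs only with 7 or fewer participants.

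**4. The 0.20 bar under the primary model.** The tested CLR is the subject-specific value at a random effect of zero (SAP 5.4.1), so step 2 does not carry over as algebra. A re-implementation of the pseudo-likelihood random-intercept model was run on deliberately adverse data: 121 participants, TP participants with several positive regions, all others with one FP region.

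| Regions per TP participant | Fewest TP participants at which CLR passes | PPV | Exact lower limit for PPV |
|---|---|---|---|
| 1 of 1 | 72 | 0.595 | 0.502 |
| 2 of 2 | 58 | 0.479 | 0.388 |
| 3 of 3 | 55 | 0.455 | 0.364 |
| 5 of 5 | 52 | 0.430 | 0.340 |
| 4 of 5 | 45 | 0.372 | 0.286 |

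In the other direction, the TP count was fixed at the largest value that fails PPV (33 of 121, 33 of 122, 40 of 152) and the region patterns were varied. The highest CLR lower limit found was 0.36, well short of 0.50.

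**5. Power at compatible values.** With 34 of 122 needed, PPV power is above 0.9999999 at a true PPV of 0.58 and above 0.999999 at 0.50. Joint power is then the CLR power: 92.7% if 152 contribute. If only PET-positive participants contribute, z = 0.08 × √(12 × 122) − 1.96 = 1.101, giving 86.5% (86.2% with 121).

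**The case against.** The strongest reply is that the success test does not use the participant-averaged CLR, which SAP 2.5.5 lists only as a sensitivity analysis. This stands. When TP participants have more positive regions than FP participants, the primary CLR can pass with PPV below one half: with 2 of 2 regions against 0 of 1, it passes at 59/122 (estimate 0.607, lower limit 0.508), where PPV is 0.484. A reader might infer that passing CLR proves PPV is above 0.50, or that PPV cannot fail once CLR passes. The documents do not support either as a theorem for the primary model. The second is a numerical finding with a wide margin.

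A crude pooled ratio could also reverse the order: 33 participants with 5/5 and 88 with 0/1 give 165/253 = 0.65 beside a PPV of 33/121 = 0.27. The plan does not test a pooled ratio.

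It is also fair that both bars must be met, so a lenient second bar cannot raise the false-positive risk; that overall power is worded as a minimum; and that PPV will be reported with its exact interval and by CTS level, so readers will see the estimate itself. All three stand. They limit the consequence but do not reconcile 0.33 with 0.58.

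It is tempting to add that the 27% benchmark is out of range because post-radiotherapy participants must be at least 2 ng/mL above nadir. Post-prostatectomy participants qualify from 0.2 ng/mL (Protocol 5.1) and the mix is not given, so that argument does not settle the matter.

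**Conclusion.** The planning values are wrong as written. Under the estimator that the sample size rests on, CLR 0.58 and PPV 0.33 cannot both hold, so the 90% PPV power and the product 0.927 × 0.90 describe no attainable scenario. Under the primary model, the 0.20 PPV bar is in practice implied by the 0.50 CLR bar: CLR was never seen to pass below a PPV of 0.37, whereas PPV fails only at 33/122 (27.0%) or fewer.

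This rests on about 121 to 122 PET-positive participants (152 at the assumed 80%), on the region patterns searched, which were not exhaustive, and on the plan's variance of 1/12, taken as given and not tested here. On that variance the 83.4% holds as a floor, since 86% and 92.7% both exceed it. Type I error is not inflated.

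A reader might also conclude that the PPV bar must rise to 0.50. Nothing in the documents supports that as a patient-level threshold. It would require 73/122, so in the 2-of-2 pattern outcomes from 59 to 72 would turn from success to failure. It is a design preference, not a correction.

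**What to change.** - **SAP 3.1 and Protocol 12.8.1:** replace the 0.33 planning value with one compatible with CLR 0.58, which means at least 0.58 under the equal-weight estimator. State PPV power at the 0.20 bar as essentially 100% and drop the product 0.927 × 0.90. Give joint power as the CLR power: 92.7% if 152 participants contribute, about 86% if only the roughly 122 PET-positive ones do, and say which applies.
- **SAP 2.5.2 and Protocol 12.4.2:** state that the 0.20 PPV criterion is effectively implied by the CLR criterion, and that meeting it will not be presented as independent evidence for the patient-level claim.

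The cost is wording in two documents. No participants, data or analyses are added, and the success rule is unchanged.
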